1. PROTOCOL SUMMARY

1.1 Schedule of Activities (SoA)

Screening Phase (Visit 1)

Subjects, or their legally acceptable representative, will provide written informed consent before any trial-specific procedures are performed. During the Screening Phase, eligibility criteria will be reviewed, and a complete clinical evaluation will be performed as specified in the Time and Events Schedule. Screening procedures will be performed within 7 days before Day 1 of therapy with olaparib. All baseline disease characteristics will be captured based on the evaluations as performed as a part of routine clinical practice in the enrolment hospital. The documented tests that are required before consideration of subject for olaparib treatment based on the local prescribing information by investigator must have been performed within 7 days before Day 1.

Treatment Phase (Visit 2-7)

The Treatment Phase will extend from Day 1 to Day 182; or until study drug discontinuation due to either disease progression or unacceptable toxicity; or other reasons whichever occurs first, as listed in the Drug Discontinuation Section. Details of the procedures performed during the Treatment Phase are outlined in the Time and Events Schedule. Subjects will be closely monitored for AEs and other safety evaluations including laboratory investigations and concomitant medications. If disease progression is diagnosed before Day 182, then the subject will discontinue study drug with completion of the End-of-Treatment Visit on the day of progression and will enter the Follow-up Phase. For visit 3 – 7, a window of \pm 3 days will be allowed per visit.

End-Of-Treatment Visit (EOT; Visit 8)

An End-of-Treatment Visit is to be scheduled on Day 182 of the study drug administration. In a case where subject discontinues the study treatment for any reason listed in Drug Discontinuation Section before Day 182, the last visit of the subject will be considered as End-of-treatment Visit. Every effort should be made to conduct the telephonic End-of-Study Visit before the subject starts subsequent treatment. For end – of – treatment visit, a window of \pm 3 days will be allowed.

Follow - Up Phase (End – Of – Study; Visit 9)

Only subjects who discontinue treatment with olaparib before end of Treatment Phase on study will be followed for 28 days after discontinuation of study drug or until the start of alternate treatment intervention, whichever is earlier. A telephone follow-up will be conducted 28 days after the EOT Visit. This will be considered as End-of-Study visit. Every effort should be made to conduct the telephone End-of-Study Visit before the subject starts subsequent treatment. For Follow – Up Phase visit, a window of \pm 3 days will be allowed.

Table 1 Study of Assessments

Study Phase	Screening Phase ^(a)	Treatment Phase					Follow-up Phase						
		On Treatment			EOT	EOS							
Cycle	1	2	3	4	5- 7	8	9						
Visit No.	1	2	3	4	5- 7	8	9						
Study Days	-6 to 0	1 (± 3 days)	15 (± 3 days)	29 (± 3 days)	57, 85 & 141 (± 3 days)	182 (± 3 days)	28 days post-EOT (± 3 days)						
Screening/Enrolment visit													
Informed consent ^(b)	Subjects must sign the informed consent form before any study-specific procedures are performed.												
Eligibility criteria	X												
Demographics/ Review medical history (including all treatments for ovarian cancer/breast cancer)	X												
WHO Performance Status	X			X	X	X	X						
General physical examination	X	Targeted physical exam (based on symptoms)											
Prior concomitant medication recording	Continuous from time of ICF until 28 days after last olaparib dose in treatment phase.												
Study drug administration													
Olaparib dosing	The recommended dose is 300 mg (150 mg X 2 tablets) twice a day												
Disease evaluations (disease characteristics will be performed as per routine clinical practice)													
Disease characteristics assessment	X			X	X								
Tumor imaging	X					X							

Study Phase	Screening Phase ^(b)	Treatment Phase					Follow-up Phase
		On Treatment			EOT	EOS	
Visit No.	1	2	3	4	5-7	8	9
Study Days	-6 to 0	1	15 (± 3 days)	29 (± 3 days)	57, 85 & 141 (± 3 days)	182 (± 3 days)	28 days post-EOT (± 3 days)
Safety evaluations							
Physical examination	X	Symptom-directed physical examination only					
Vital sign parameters	X	X			X	X	
ECG	X	Performed if clinically indicated					
Adverse event monitoring	Continuous from time of ICF until 28 days after last olaparib dose in Treatment Phase and Follow-up Phase if eligible.						
Haematology & Biochemistry ^[c]	X	X	X	X	X	X	X
Hepatitis B and C	X						
Pregnancy Test	X	X	X	X	X	X	X
PT/INR	X	X	X	X	X	X	X
Comprehensive serum chemistry panel	X	X	X	X	X	X	X
Urinalysis	X	X	X	X	X	X	X

Footnotes:

EOT = End-of-Treatment. EOS = End-of-Study. ICF = informed consent form.

- The Screening Phase begins when the first screening procedure is conducted. Screening tests should be performed within 7 days of Day 1 except for disease evaluations (performed as routine clinical practice).
- Must be signed before first study-related activity.
- Haematology and biochemistry as described in the Safety Evaluations section

1.2 Synopsis

National Co-ordinating Investigator

Name: PPD

Title: PPD

Address: PPD

Email: PPD

Protocol Title: A Prospective, Multicentre, Phase-IV Clinical Trial of Olaparib in Indian Patients with Platinum Sensitive Relapsed Ovarian Cancer who are in Complete or Partial Response Following Platinum Based Chemotherapy and Metastatic Breast Cancer with Germline BRCA1/2 Mutation (SOLI Study)

Short Title: Phase IV Study of Olaparib in Indian Patients

Rationale:

Objectives and Endpoints

Primary objective:	Endpoint/variable:
To assess the safety of olaparib in Indian subjects with: 
• platinum sensitive relapsed ovarian cancer who are in complete or partial response following platinum-based chemotherapy, and• HER - 2 negative metastatic breast cancer with germline BRCA1/2 mutation.	Number, frequency and proportion of subjects with adverse events (AEs) and serious adverse events (SAEs). The safety variables to be analysed include AEs, clinical laboratory tests (haematology and chemistry), physical examination results, vital parameters, World Health Organization (WHO) performance status (PS), and deaths as observed by participating physician.

Overall design: This is a prospective, single - arm, multicentre, interventional phase – IV trial investigating the safety of olaparib in Indian adult subjects receiving olaparib as per the local approved prescribing information.

Study Period:

Table 2 Study Timelines

Total planned Study period	
Estimated date of first subject in	March 2020
Estimated date of last subject in	March 2021
Estimated date of last subject last visit	October 2021
Estimated date of data base lock	December 2021

Number of Subjects:

No. of total screened subjects: Approximately 225 (180 for Ovarian and 45 for Breast)

No. of total enrolled subjects: Approximately 200 (160 for Ovarian and 40 for Breast)

No. of study sites: 15

Treatments and treatment duration: Single arm study. Study Subjects will receive Olaparib tablets 300 mg (150 mg X 2) BD

Data Monitoring Committee: As constituted by the Principal Investigator/ National co-ordinating investigator.

[figure not shown]
Statistical methods

There is no formal sample size calculation as this study is being conducted as a regulatory requirement for a phase IV study including Indian patients in the approved indications post marketing of olaparib.

1.3 Schema

The general study design is summarised in Figure 1.

Figure 1 **Study design**

EOT: End of Treatment; EOS: End of Study

2. INTRODUCTION

2.1 Background and study rationale

In India, ovarian cancer is the third leading site cancer among women next to cervical and breast cancers. In India, incidence of ovarian cancer as reported in various population based registries ranges between 1.7 to 15.2 (age-adjusted incidence rate per 100,000 population) between 2012-14 (National Cancer Registry Programme, 2016a). Incidence of ovarian cancer is increasing from 1982 till date in India. Projected burden of ovarian cancer in India was 45,231 subjects in 2015 and is estimated to touch 59,000 subjects in 2020 (National Cancer Registry Programme, 2016b). Similarly, projected cases of ovarian cancer mortality in India during 2021 and 2026 is approximately 17000 and 20000, respectively (D'Souza et al., 2013). Ovarian cancer is therefore an important public health issue in India.

The prognosis of ovarian cancer is worst among all gynecological malignancies with the 5-year survival rate of 46% across all stages and 27% for advanced stages in USA (Siegel et al., 2017). Poorer outcomes are noted in other developing economies too. This is more evident in a country like India where the patients present in advanced stages and chances of optimal treatment are bleak. Due to detection in late stages of disease the recurrence is common and eventually death follows. The overall 5-year survival rate was 16 % during the period of 2010-14 in India (Allemani et al., 2018).

The proportion of breast cancer cases in India has been steadily increasing in the past few decades and in 2012, breast cancer dethroned cervical cancer as the commonest cause of cancer among women in India (Rangarajan et al., 2016). It is estimated that in 2015, 155,000 patients were affected with breast cancer in India (Rangarajan et al., 2016). While the presentation of breast cancers in India is similar to the western countries in early stages, there is a considerably higher number of Indian patients presenting with triple negative breast cancers in advanced stages (Sandhu et al., 2016). In India, 5-year survival rate for patients with breast cancer was 66 % during the period of 2010-14 (Allemani et al., 2018) compared to the western countries like USA which have a 5 – year survival rate of > 90 %. Also, it is imperative to note that stage IV (metastatic) breast cancers have a 5 – year survival of only 22 % in Indians (Agarwal and Ramakant, 2008). Approximately 5 % of the patients with breast cancer harbour germline BRCA mutations (gBRCAm) (Farmer et al., 2005; Murai et al., 2012). These mutations are more likely to be present in patients who are younger, with strong family history of breast cancer and those patients who are estrogen receptor (ER)/ progesterone receptor (PR) negative and human epidermal growth factor receptor – 2 (HER2) negative (triple negative) (Farmer et al., 2005; Murai et al., 2012). Olaparib (Lynparza®) is an inhibitor of the mammalian polyadenosine 5'-diphosphoribose polymerase (PARP) enzyme. When olaparib is bound to the active site of DNA associated PARP it prevents the dissociation of PARP and traps it on the DNA, thus blocking repair (Bryant et al., 2005). In replicating cells, this leads to DNA double strand breaks (DSBs) when replication forks meet the PARP DNA adduct. In normal cells, homologous recombination repair (HRR), which requires functional BRCA1 and 2 genes, is effective at repairing these DNA double strand breaks (Ashworth, 2008; Shin et al., 2004). In the absence of functional BRCA1 or 2, DNA DSBs cannot

be repaired via HRR. Instead, alternative and error-prone pathways are activated, such as the non-homologous end joining (NHEJ) pathway, leading to increased genomic instability. After many rounds of replication genomic instability can reach insupportable levels and result in cancer cell death, as cancer cells have a high DNA damage load relative to normal cells (Ashworth, 2008; Farmer et al., 2005; Shin et al., 2004).

Lynparza® tablet is currently approved in USA for (A) maintenance treatment of adult patients with recurrent epithelial ovarian, fallopian tube or primary peritoneal cancer, who are in a complete or partial response to platinum-based chemotherapy; (B) the treatment of adult patients with deleterious or suspected deleterious gBRCAm advanced ovarian cancer who have been treated with three or more prior lines of chemotherapy; and (C) in patients with deleterious or suspected deleterious gBRCAm, HER2-negative metastatic breast cancer, who have been treated with chemotherapy in the neoadjuvant, adjuvant, or metastatic setting (USFDA, 2017).

The 69th meeting of the Oncology and Haematology Subject Expert Committee held in April 2018 has given positive recommendations for approval of olaparib as monotherapy with a condition to conduct phase IV clinical trial as per the requirements of Indian Good Clinical Practices (GCP) and schedule Y of Drugs and Cosmetics Rules, 1945 (Drug Controller General (India), 2018). Subsequently, the Drugs Controller General of India (DCGI) has provided market authorization for olaparib in the following indications: (A) for the maintenance treatment of adult patients with recurrent epithelial ovarian, fallopian tube or primary peritoneal cancer, who are in a complete or partial response to platinum-based chemotherapy; (B) for the treatment of adult patients with deleterious or suspected deleterious gBRCAm advanced ovarian cancer who have been treated with three or more prior lines of chemotherapy; and (C) in patients with deleterious or suspected deleterious gBRCAm, HER2-negative metastatic breast cancer who have previously been treated with chemotherapy in the neoadjuvant, adjuvant or metastatic setting. Patients with hormone receptor (HR)-positive breast cancer should have been treated with a prior endocrine therapy or be considered inappropriate for endocrine treatment (Drugs Controller General (India), 2018).

The approval for olaparib in ovarian cancer is based on Study 19 (n = 265), Study 42 (n = 137) and SOLO2 (n = 295). Study 19, a phase II study, which included patients irrespective of their BRCA status, showed a significant progression free survival (PFS) benefit (8.4 vs 4.8 months) over placebo with a hazard ratio of 0.35, p <0.0001 (Ledermann et al., 2012). There is now long term safety and efficacy data of the patients enrolled in Study 19 with 15 patients (11%) on the study drug for >6 years which included an equal proportion of gBRCAm as well as non – BRCA mutated patients (Gourley et al., 2017). In Study 19 (dose of olaparib used in the study was 400 mg BD in Capsule formulation), common grade 3 or worse adverse events in the olaparib group were fatigue (8%) and anaemia (6%). 22 % patients in the olaparib group reported serious adverse events.(Ledermann JA , et al, 2016) The phase III SOLO2 study which included only gBRCAm patients with ovarian cancer in the maintenance management of ovarian cancer, showed a significant PFS benefit over placebo (19.1 vs 5.5 months; HR of 0.30, p <0.0001) (Pujade-Lauraine et al., 2017). In the SOLO – 2 study (dose of olaparib used in the study was 300 mg BD in tablet formulation), serious adverse events were experienced by 18 % patients in the olaparib group compared to 8 % patients in the placebo group. The most common in the olaparib group were anaemia (4 % patients), abdominal pain (2% patients), and intestinal obstruction (2 % patients)

(Pujade-Lauraine et al., 2017). In the third-line or later treatment indication of olaparib, the approval is based on the results of the phase II study 42 (n = 137), which, in gBRCAm patients showed an ORR of 34% (Domchek et al., 2016; Matulonis et al., 2016). In Study 42, Grade ≥ 3 AE's were observed in 55 % of the patients with the commonest ones being anaemia (20 %), abdominal pain (8 %) and fatigue (7 %). (Domchek et al., 2016)

The approval of olaparib for patients with metastatic breast cancer was based on the OlympiAD trial (n=302) which showed a significantly better median PFS of 7 months compared to 4.2 months in the standard chemotherapy arm (capecitabine, eribulin mesylate or vinorelbine). This translates to a 42 % reduction in risk of progression or death in the olaparib arm (Robson et al., 2017). The PFS benefit with olaparib appeared to be more marked in patients with triple negative breast disease as compared to those with HER-2 negative and HR positive disease on prespecified subgroup analysis (Robson et al., 2017). In the OlympiAD study, grade 3 or higher adverse events were observed in 36.6 % in the olaparib group and 50.5% in the standard-therapy group, and the rate of treatment discontinuation due to adverse effects was 4.9 % and 7.7 %, respectively

As per recommendation from DCGI, the current phase-IV study is planned with the aim to assess the safety in Indian subjects receiving olaparib as per the approved label indications in India in accordance with the requirements of the Health Authorities of India. This study attempts to descriptively elucidate the safety of Olaparib in Indian subjects receiving olaparib as per the Indian regulatory approved indications in India. The data obtained from the present study will help to understand the safety profile of olaparib in Indian patients.

2.2 Benefit/risk assessment

This study attempts to capture and elucidate the safety of Olaparib in Indian Subjects. After due consideration to the facts that global clinical trials with Lynparza have not included subjects from India and also, to fulfil the regulatory requirement for the approval of Lynparza, this study's results will be one of the first reports of the safety of Olaparib in Indian patients. The common side effects of Olaparib include nausea, anaemia, fatigue and abdominal pain. However, considering the small sample size of this study and the fact that this study is not powered to compare the safety of this study population versus that seen in the global clinical trials, it is possible that certain adverse events may be under or over – represented. No effort will be made to statistically compare the side effects observed in this study with that seen in the global clinical trials with Olaparib.

3. OBJECTIVES AND ENDPOINTS

Table 3 Study objectives

Primary objective:	Endpoint/variable:
To assess the safety of olaparib in Indian subjects with: 
platinum sensitive relapsed ovarian cancer who are in complete or partial response following platinum-based chemotherapy, andHER - 2 negative metastatic breast cancer with germline BRCA1/2 mutation.	Number, frequency and proportion of subjects with adverse events (AEs) and serious adverse events (SAEs). The safety variables to be analysed include AEs, clinical laboratory tests (haematology and chemistry), physical examination results, vital parameters, World Health Organization (WHO) performance status (PS), and deaths as observed by participating physician.

4. STUDY DESIGN

4.1 Overall design

This is a prospective, single - arm, multicentre, interventional phase – IV trial investigating the safety of olaparib in Indian adult subjects receiving olaparib as per the local approved prescribing information. The investigator will be trained on the locally approved prescribing information before the enrolment of the first subject at their site to ensure compliant and proper dosing of the study drug.

The decision of subjects to participate in this study must not, in any way, impact upon the standard of care that they are receiving or any benefits to which they are otherwise entitled. Prior to data collection, all subjects must sign an informed consent form (ICF) allowing data collection and source data verification in accordance with local requirements and sponsor policy. Subjects who are prescribed olaparib by an independent clinical judgement of investigator in his/her routine practice based on locally approved prescribing information will be eligible for screening under this study. To enrol approximately 200 subjects (160 patients to be enrolled in the ovarian cancer indication and 40 from the breast cancer indication), it is expected that approximately 225 subjects (180 patients with ovarian and 45 patients with breast cancer) will be screened.

Subjects will be monitored throughout the study period for AEs of olaparib.

Subject participation will include a Screening/Enrolment Phase, a Treatment Phase, and a Follow-up Phase. The Screening/Enrolment Phase will be up to 7 days prior to Day 1. The Treatment Phase will extend from Day 1 to Day 182; or until study drug discontinuation due to either disease progression or unacceptable toxicity; or other reasons as listed in Drug Discontinuation Section, whichever occurs first. The Follow-up Phase will begin once a subject discontinues study drug during Treatment Phase, and will continue until 28 days after last dose, death, loss to follow - up, consent withdrawal for study participation, or study end, whichever occurs first (see section 7). Subjects who are observed to continue to receive clinical benefit from olaparib at end of Treatment

Phase (as defined in SoA) will continue treatment in Extension Phase (defined in section 6.7) as long-term clinical benefit is observed or until the investigator decides it is not in the best interest of the subject to continue olaparib treatment.

Safety will be evaluated throughout the evaluation phase and during the follow - up of subjects who discontinue treatment before end of Treatment Phase by physical exams including vital signs, AE/SAE monitoring, laboratory evaluations and recording of concomitant medications. The sponsor shall provide the laboratory investigations for safety evaluation including haematology and biochemistry as mentioned in the Time and Events Schedule to monitor the safety throughout the study period. A window period of +/- 3 days will be allowed for visits 3 – 9.

Screening Phase (Visit 1)

Subjects, or their legally acceptable representative, will provide written informed consent before any trial-specific procedures are performed. During the Screening Phase, eligibility criteria will be reviewed, and a complete clinical evaluation will be performed as specified in the Time and Events Schedule. Screening procedures will be performed within 7 days before Day 1 of therapy with olaparib. All baseline disease characteristics will be captured based on the evaluations as performed as a part of routine clinical practice in the enrolment hospital. The documented tests that are required before consideration of subject for olaparib treatment based on the local prescribing information by investigator must have been performed within 7 days before Day 1.

Treatment Phase (Visit 2-7)

The Treatment Phase will extend from Day 1 to Day 182; or until study drug discontinuation due to either disease progression or unacceptable toxicity; or other reasons whichever occurs first, as listed in the Drug Discontinuation Section. Details of the procedures performed during the Treatment Phase are outlined in the Time and Events Schedule. Subjects will be closely monitored for AEs and other safety evaluations including laboratory investigations and concomitant medications. If disease progression is diagnosed before Day 182, then the subject will discontinue study drug with completion of the End-of-Treatment Visit on the day of progression and will enter the Follow-up Phase.

End-Of-Treatment Visit (EOT; Visit 8)

An End-of-Treatment Visit is to be scheduled on Day 182 of the study drug administration. In a case where subject discontinues the study treatment for any reason listed in Drug Discontinuation Section before Day 182, the last visit of the subject will be considered as End-of-treatment Visit. Every effort should be made to conduct the telephonic End-of-Study Visit before the subject starts subsequent treatment.

Follow - Up Phase (End – Of – Study; Visit 9)

Only subjects who discontinue treatment with olaparib before end of Treatment Phase on study will be followed for 28 days after discontinuation of study drug or until the start of alternate treatment intervention, whichever is earlier. A telephone follow-up will be conducted 28 days after the EOT Visit. This will be considered as End-of-Study visit. Every effort should be made to conduct the telephone End-of-Study Visit before the subject starts subsequent treatment.

For an overview of the study design see Figure 1, Section 1.3. For details on treatments given during the study, see Section 6.1 Treatments Administered.

For details on what is included in the study endpoints, see Section 3 Objectives and Endpoints.

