7.1.2 Procedures for discontinuation of study treatment

The investigator should instruct the subject to contact the site before or at the time if Study treatment is stopped. A subject that decides to discontinue Study treatment will always be asked about the reason(s) and the presence of any AEs. The date of last intake of Study treatment should be documented in the eCRF. All Study treatment should be returned by the subject at their next on-site study visit or unscheduled visit. Subjects permanently discontinuing Study treatment should be given locally available standard of care therapy, at the discretion of the Investigator.

Discontinuation of Study treatment, for any reason, does not impact on the subject's participation in the study. The subject should continue attending subsequent study visits and data collection should continue according to the study protocol. If the subject does not agree to continue in-person study visits, a modified follow-up must be arranged to ensure the collection of endpoints and safety information. This could be a telephone contact with the subject at 28 days post discontinuation

(End of Study Visit as described in SoA), a contact with a relative or treating physician, or information from medical records. The approach taken should be recorded in the medical records. A subject that agrees to modified follow-up is not considered to have withdrawn consent or to have withdrawn from the study.

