8.3.2 Time - period and frequency for collecting AE and SAE information

Adverse Events will be collected continuously from time of ICF until 28 days after last olaparib dose in Treatment Phase and Follow-up Phase.

All SAEs will be recorded and reported to the sponsor or designee within 24 hours, as indicated in Appendix B. The investigator will submit any updated SAE data to the sponsor within 24 hours of it being available.

Investigators are not obligated to actively seek AE or SAE in former study subjects. However, if the investigator learns of any SAE, including a death, at any time after a subject's last visit and he/she considers the event to be reasonably related to the Study treatment or study participation, the investigator may notify the sponsor.

The method of recording, evaluating, and assessing causality of AE and SAE and the procedures for completing and transmitting SAE reports are provided in Appendix B.

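### The End-of-Study call is timed from an End-of-Treatment visit that may precede the last olaparib dose, while the adverse event period is timed from the last dose

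*Protocol*

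**What the plan says.** Sections 1.1 and 4.1 schedule the EOT visit for Day 182. For a subject who discontinues earlier, for any listed reason, "the last visit of the subject will be considered as End-of-treatment Visit". The next paragraph times the final contact from it: "A telephone follow-up will be conducted 28 days after the EOT Visit. This will be considered as End-of-Study visit". Table 1 agrees, giving Visit 9 as "28 days post-EOT (± 3 days)".

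For one reason the EOT visit is fixed to the stop. On progression, "the subject will discontinue study drug with completion of the End-of-Treatment Visit on the day of progression". The other reasons in section 7.1, such as an adverse event, withdrawn consent for the drug or non-compliance, have no such rule.

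The safety period has another anchor. Section 8.3.2 states: "Adverse Events will be collected continuously from time of ICF until 28 days after last olaparib dose in Treatment Phase and Follow-up Phase". The description of the Follow-up Phase in 4.1 and the AE summaries in 9.4.2 also run to 28 days after the last dose. Section 7.1.2, on modified follow-up, says "This could be a telephone contact with the subject at 28 days post discontinuation" and labels that contact the End-of-Study visit of the schedule. Section 7.3 gives a further timing for that visit: Day 182, or 28 days from study withdrawal.

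**The concern.** The two anchors agree only if the EOT visit coincides with the last dose. A subject who stops at home between visits may have as her most recent visit one at which she was still taking olaparib. If that visit is relabelled EOT, its laboratory, vital-sign and performance-status results predate the stop, and the call is counted from a date before the last dose.

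This matters because safety is the only objective and the endpoint is the number and proportion of subjects with AEs and SAEs. Under section 4.4, completing the End-of-Study visit completes the study for that subject. Section 8.3.2 then releases the investigator from actively seeking events in former subjects, and 8.3.3 ends CRF recording of AEs unresolved at the last assessment. An early call can therefore close active ascertainment while the period defined in 8.3.2 and 9.4.2 is still open. Table 1 marks laboratory tests at Visit 9, but that visit is a telephone contact, so those marks do not by themselves secure a sample.

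**Working it through.** The plan states no figure to reproduce; the check is date arithmetic on the schedule.

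**Inputs.** Visit days 1, 15, 29, 57, 85, 141 and 182 (Table 1). Call at EOT + 28 days, ±3 (1.1, 4.1, Table 1). AE period to last dose + 28 days (4.1, 8.3.2, 9.4.2).

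**Formula.** Let V be the last attended visit and X the last dose, with X after V and before the next visit. On the literal rule:
- EOT = V, so the call is due at V + 28
- the AE period ends at X + 28
- shortfall = (X + 28) − (V + 28) = X − V
- the call falls due before the last dose when X − V > 28

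**Largest nominal shortfall in each gap** (last dose on the day before the next visit):

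| Gap (days) | Length | Call due | AE period ends | Shortfall |
|---|---|---|---|---|
| 1–15 | 14 | 29 | 42 | 13 |
| 15–29 | 14 | 43 | 56 | 13 |
| 29–57 | 28 | 57 | 84 | 27 |
| 57–85 | 28 | 85 | 112 | 27 |
| 85–141 | 56 | 113 | 168 | 55 |
| 141–182 | 41 | 169 | 209 | 40 |

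**Example.** Last visit Day 85, last dose Day 105. The call is due on 85 + 28 = Day 113, which is 8 days after the last dose. The AE period ends on 105 + 28 = Day 133. The shortfall is 133 − 113 = 20 days.

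**Due dates already past.** The call falls due before the last dose for last doses on Days 114–140 (27 days) and Days 170–181 (12 days). That is 27 + 12 = 39 of the 175 non-visit days between Day 1 and Day 182. At nominal visit times this occurs only in the two longest gaps. For these subjects the rule yields a date already past when the drug is stopped, so it gives no usable date for the call.

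**Window alone.** With EOT on the day of the last dose, the earliest permitted call is 28 − 3 = day 25, leaving up to 3 of 28 days (11%) after the call.

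**With both anchored to the last dose,** X − V plays no part and the shortfall is 0 before any window is applied.

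**The case against.** The strongest reply is that the protocol, read as a whole, intends the right thing. Directly before the sentence on the call, 1.1 and 4.1 say that early stoppers are followed for 28 days from discontinuation. Section 7.1.2 asks the subject to contact the site before or when she stops, to keep attending visits, and to return tablets at the next on-site or unscheduled visit. On a natural reading that later visit is her last visit and hence her EOT. Section 4.1 also lists examinations, vital signs and laboratory evaluations during follow-up of early stoppers, 7.1 refers to the schedule for data at discontinuation, and 8.3.2 requires AE collection to 28 days after the last dose whatever the date of the call.

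Much of this stands. A reader might infer that early stoppers have no laboratory or vital-sign assessment after stopping, or that their events are under-counted. The documents support neither: the sections just named foresee such assessments, and nothing shows that events are lost.

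A reader might also turn the gaps into an expected effect. If stops were spread evenly over Days 1 to 182, the mean lag from last visit to stop would be (14² + 14² + 28² + 28² + 56² + 41²) / (2 × 181) = 6777/362 = 18.7 days. That describes an assumption, not this trial: it needs every stop to fall between visits with no visit afterwards. Several reasons in 7.1 are determined by the investigator, so the stop may well coincide with a visit. Where treatment ends after a hold of more than 21 days, the last dose precedes the decision by weeks, and an EOT visit near the decision makes the call late rather than early.

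What the reply does not do is amend the rule. Section 7.1.2 offers the call 28 days after discontinuation as one possible form of modified follow-up, while 1.1, 4.1 and Table 1 still count from EOT. Section 8 makes adherence to the schedule essential. Sites reading these passages differently would observe different periods.

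**Conclusion.** The point holds as a contradiction in a stated rule. The End-of-Study call is anchored to an EOT visit that, except on progression, need not be at or after the stop, while the AE period is anchored to the last dose. On the literal rule the call can fall due before the AE period closes by the time since the last visit, nominally up to 55 days; the −3-day window alone allows up to 3. The 55 days is the distance between two dates that the plan sets, not a measured loss of follow-up.

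The size rests on the nominal visit days and on reading last visit as the most recent visit attended before the stop. How many subjects this would affect cannot be derived from the protocol. A missed assessment or an under-count in a particular subject is possible but not shown. The case for acting is that the endpoint's observation period should be unambiguous in a single-arm safety study, and that clarity costs little here.

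**What to change.** Reconcile the passages in 1.1, 4.1 and Table 1:

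- Time the End-of-Study call from the date of the last dose, the anchor that 8.3.2 and 9.4.2 already use, and align 7.1.2 and 7.3 with it.
- Give the call a one-sided window, for example 0 to +3 days, so that it cannot precede day 28.
- State that for an early stop the EOT visit is the first on-site or unscheduled visit at or after the stop. Section 7.1.2 already foresees such a visit for drug return.

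The cost is wording, calls up to 3 days later, and for some early stoppers EOT assessments at the drug-return visit. The change concerns only the timing of assessments.
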